Subjects will be randomized in a 1:1 ratio to either treatment or sham group. Randomization will be determined using a computer program based on random number generation in blocks of 10 subjects at a time. The manufacturer will provide the researchers with four devices per package (4 weeks per patient) and distribute 10 packages at a time to the investigators. Each package will have a serial number and only one research coordinator will have the key to which serial numbers represent active devices and which represent inactive ones. This research coordinator will keep the data in a secure database and will not be involved in any of the patient recruitment or study procedures. All other research coordinators, investigators, statistician and nurses involved will be blinded. Research coordinators within the division of gastroenterology will store the devices as pre-packaged by manufacturer and label the devices with a serial number and patient ID number. A labeled folder for each patient with all questionnaires needed for the entire study will also be kept with each subject package. The devices and folders will be stored in a locked office in the gastroenterology division, only accessible by research coordinators. Password protected iPads will be used to collect questionnaire information from participants. No PHI will be loaded on these iPads.

A blinded research coordinator will bring each subject's numbered package to the research area (Translational Research Unit) when patient arrives. The package for the subject will be stored locked in the TRU until the subject finishes the 4 week therapy. The coordinator will ask the subject to complete the pre-placement questionnaires (Table 1; visit #3) and hand the device (numbered with serial # and patient ID only) to one of the certified MDs for placement. The devices will be "made to order" when requested by the PI and will be shipped packaged as above.

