Patients will be told that they may or may not feel a slight flushing or tingling sensation after device placement. The electrode/needle arrays are implanted according to the individual's arterial and cranial nerve anatomy. The exact location of the implantation may vary slightly from person to person but is determined by both knowledge of auricular neuro-anatomy and visualization of the neurovascular bundles by trans-illumination (IHS, Versailles, IN, USA). The points will be targeted by four-point electrical stimulation using the EAD device after carefully disinfecting the ear. The small device will be positioned and secured behind the ear similar to a hearing aid, which may be covered by hair. Neurostimulation will be delivered below sensation threshold continuously for 5 consecutive days. The EAD device will be applied by a trained MD. Subjects will remove the device independently at home and discard them as they are non-functioning after 5 days (5 days battery life). If a device is lost or broken, the research team will attempt to schedule placement of a new EAD within 1 day if you wish. The devices are easily removed by removing the tapes and adhesives. Before and during the treatment trial, subjects and parents will complete questionnaires as shown in Table 1.

The EAD Surgical kit consists of :

- an alcohol swab
- prep and stay swab
- round fixation plasters
- fixation plasters to fasten the generator
- Steri-strip adhesive vial
- Sterile wire harness pack
- Generator
- Tweezers
- Surgical marker
- Transilluminator

EAD placement details:

1. A research coordinator in the GI office will be asked to open the package and obtain either a true device or a control device as outlined in a randomization scheme provided by the statistician. This research coordinator will document the patient ID, name and the device serial number in the study database and whether assigned to an active vs inactive device. This lead research coordinator will be the only unblinded person and she will not be involved in any patient contact or other parts of the study.

2. The neurostimulator placement will be performed as directed and per EAD training protocol instructions identically to prior CHW IRB approved trial.

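### The statistician is declared blinded but supplies the scheme from which real or sham devices are drawn, so that blinding is not delivered as written

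*Combined protocol and SAP*

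**What the plan says.** Two parts of Section F of the combined protocol and SAP deal with who knows allocation.

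The randomisation text under Auricular Neurostimulation (EAD) treatment protocol sets the ratio and method: "Subjects will be randomized in a 1:1 ratio to either treatment or sham group", and "Randomization will be determined using a computer program based on random number generation in blocks of 10 subjects at a time". It does not say who runs the program. Device packages arrive from the manufacturer with serial numbers, and "only one research coordinator will have the key to which serial numbers represent active devices and which represent inactive ones". It then states: "All other research coordinators, investigators, statistician and nurses involved will be blinded".

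EAD placement details, step 1, describes how a device is chosen. The coordinator is to open the package and take either a real or a sham device "as outlined in a randomization scheme provided by the statistician". The same coordinator must "document the patient ID, name and the device serial number in the study database and whether assigned to an active vs inactive device". The step ends with the assurance: "This lead research coordinator will be the only unblinded person".

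**The concern.** A scheme that tells its user whether to take a real or a sham device is the allocation sequence. The person who provides it has had that sequence, yet the randomisation text lists the statistician among the blinded, and step 1 allows for one unblinded person only. As written, there are two.

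What is at stake is the independence of the analysis. The Statistical Analysis part of Section F leaves several decisions until the data have been seen. Keeping the analyst unaware of allocation is the usual protection for such decisions, and the plan claims that protection. If the person who supplied the scheme also makes the decisions, the protection is absent.

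**Working it through.** No arithmetic applies, because the point rests on no sample size, power or error rate. The check sets the statements side by side.

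1. **Stated status.** The randomisation text says the statistician is blinded.
2. **Stated number unblinded.** Step 1 says one person, the lead coordinator.
3. **Stated source of the scheme.** Step 1 says the statistician provides it, and describes it by device type. It mentions no codes.
4. **Consequence.** Item 3 gives the statistician the sequence, which conflicts with items 1 and 2 unless the scheme is masked.
5. **Does the serial-number key resolve this?** Only in part. The key links a serial number to a device type, and the statistician is not said to hold it. A list written as real or sham does not need it: the first entry belongs to the first subject randomised, the second to the second, and so on. Anyone with the list and the order of randomisation can recover allocation. The documents do not say whether the statistician has that order, and they do not rule it out.
6. **Does anything else resolve it?** The documents mention only one statistician. They describe no independent statistician, no masked arm labels for the analysis and no point at which the models are fixed before unblinding. The account of manufacturer-supplied, serial-numbered packages also fits poorly with a coordinator choosing device type from a statistician's list, so it is unclear who generates and who holds the sequence.
7. **Which decisions are exposed?**
   - Whether to transform or to use a non-parametric test is settled after looking at the data (Missing Data Handling; Continuous/Ordinal variables).
   - Interactions for the regression models are identified with CART (Missing Data Handling).
   - The test of the primary outcome is open. The Power text for Aim 3 compares pre and post scores by paired t-test, while Longitudinal Continuous Variables sets out a mixed model for repeated measures and calls it primary.
8. **Which decisions are not exposed?** The mixed model's fixed effects and its unstructured covariance are named in advance. Other covariance structures are to be tried only to explore fit.

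**The case against.** The strongest reply is that the two parts can be reconciled. Providing a scheme is not the same as keeping it or being able to link it to subjects. Packages are identified by serial number and patient ID only, and one coordinator holds the key. Nor do the documents say that this statistician analyses the data: Section J has the principal investigator supervise analysis, Section O names only software, and the database is maintained by a separate department.

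Part of this stands. Access to allocation at the time of analysis is a possibility, not a stated fact. What does not stand is that the text already protects against it. Step 1 describes the scheme by device type, and the serial-number key does not mask a list of that kind. If a coded list was intended, saying so is the remedy.

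A reader might draw three stronger conclusions, none of which the documents support.

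- **That the double-blind description fails altogether.** A statistician holding a list does not unblind subjects, placing physicians or nurses. The primary outcome is a subject-completed nausea scale, and subjects are asked to guess their allocation as a test of blinding.
- **That the type I error is inflated by a calculable amount.** A figure of the form 1 − 0.95^k is the chance that at least one of k independent two-sided tests falls below 0.05. The documents give no k, and tests on the same subjects and endpoint are correlated. An analyst who saw only codes A and B could still pick the smallest two-sided p-value. Such a figure measures lack of prespecification, not lack of masking.
- **That CART chooses the covariates and the covariance structure is open.** CART is used to find interactions. The regression covariates are given as demographics, baseline values and overall symptoms, and the primary covariance structure is named.

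**Conclusion.** The point holds as an internal contradiction in a core safeguard: the plan states that the statistician is blinded, then gives the statistician the role of providing the allocation scheme. That much follows from the text alone.

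The effect on the analysis is conditional. It requires that the provider of the scheme also analyses the data and can place subjects in randomisation order, and the documents state neither. On those assumptions the exposure is limited to transformation or test choice, CART-identified interactions, and which of two analyses is treated as primary. The size of any bias cannot be derived from the documents, so none is given. The point shows opportunity, not bias or misconduct. It should be corrected before allocation is revealed.

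**What to change.** Change EAD placement details, step 1, so that the statistician issues the list in codes A and B only. The manufacturer, or the already unblinded coordinator, assigns which code is active and keeps that key. Having the coordinator generate the sequence as well would be a poorer solution, because one person would then generate, hold and carry out the allocation.

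State in the Statistical Analysis part that the analyst sees only A/B until the primary model, the transformation rule and the choice between paired t-test and mixed model are fixed in writing. This second sentence is essential, since coded arms alone do not prevent selection among analyses.

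Then make the randomisation text and step 1 agree on who generates the sequence, who holds it and who is unblinded. The cost is a few sentences, with no extra staff.

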Research-dedicated GE MR750 3.0 Tesla whole-body scanners with 32-channel phase-array head coil will be employed and the scanner is located in the Froedtert Hospital (FH)/Medical College of Wisconsin (MCW). Our scanning protocol will focus on integrating the most recent advances in multimodal imaging technologies, including T1 SPGR, T2 FLAIR, R-fMRI, and ASL-CBF images. The justifications of utilizing these imaging protocols are: 1) to noninvasively characterize the structural, functional, and metabolic changes in subjects; 2) these imaging protocols will provide robust quality control, repeatable and reliable imaging datasets for imaging post-processing and statistical analyses; 3) most of these imaging protocols and pulse sequences have been tested and released as products by major scanner vendors (GE, Siemens, and Philips), therefore, they can be immediately translatable to the clinic setting.

Specifically, the integrated multimodal imaging protocols and justification are summarized below:

1) SPGR high-resolution images. Acquire T1 weighted spoiled gradient recalled echo (SPGR) images for high spatial resolution of anatomical images. The SPGR images can be employed for tissue segmentation and volumetric analysis using FreeSurfer, and image registration for functional neural network studies.

2) FLAIR images. Acquire T2 weighted fluid attenuated inversion recovery (FLAIR) images for general pathological detection such as for macroscopic white matter lesion quantification, and micro hemorrhage. In addition, the T1/T2 ratio can provide myelination information.

3) R-fMRI images. Acquire resting state functional magnetic resonance imaging (R-fMRI) datasets to study intrinsic blood oxygenation level dependent (iBOLD) signal. These iBOLD signals will be employed to study changes in neural networks of the disease and control brains. It is hypothesized that a) alterations in functional cortical networks are apparent; b) Network wide analysis can identify and classify functional disease status together with their comorbidity. We will utilize “seed”-based, module-based, and whole brain network-based analyses to characterize the changes in nausea/pain brains. For the image acquisition, we will employ our newly developed pulse sequence, named Spatially compensated Intra-shot Turbo keyhole (SCITH), based on multi-echo denoise approach for robust reliability and repeatability for functional connectivity analyses.

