All these imaging protocols and data acquisition will be completed within one scanning sessions in 30 min for each subject.

Data Acquisition and Analysis

Data acquisition: The cerebral cortical activity will be monitored in all subjects with a blood oxygenation level-dependent (BOLD) fMRI technique. Gradient echo-planar imaging (EPI) data will be acquired on a Neuro-optimized 3.0 T MR system (General Electric, Milwaukee, WI, USA). A quadrature birdcage head coil will be used for radio frequency (RF) transmission and reception. One hundred and twenty T2*- weighted images depicting blood oxygenation level-dependent (BOLD) contrast (Ogawa et al., 1990) will be acquired over 6 min at each of 14 near-axial non-contiguous 4 mm thick planes parallel to the inter commissural (AC±PC) line: TE (echo time) = 25 ms; TR (repetition time) = 2 s; matrix size = 64 x 64; FOV (Field of view) = 240 mm; in-plane resolution = 3.75*3.75 mm²; interslice gap = 0.7 mm.

Scanning protocol: A 6 min resting state scan will be performed at baseline. The same protocol is repeated at end of therapy with another scan after device is removed (Table 1; post-neurostimulation #1). This will allow us to examine functional connectivity changes induced by the stimulation. rsFC will be compared between baseline and end of treatment in both treatment responders and non-responders and compared to healthy controls and IBS patients. Brain activation will be quantified for each voxel by measuring percent change of BOLD signal relative to the baseline. Spatial smoothing of the response magnitude across voxels will be

conducted using a 6-mm full-width half-maximum (FWHM) Gaussian kernel filter to compensate for intersubject variability. In the group analysis, activation maps for each stimulation state and group will be derived by applying voxelwise one-sample *t*-tests of fitting coefficient from regression analysis. The obtained statistical maps were corrected for multiple comparisons using the probability and cluster thresholding technique (AlphaSim in AFNI).

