Strategies for imaging data analysis and data fusion with clinical observation. The goal for analyzing results from integrated multimodal imaging protocols is provide structural, functional, and metabolic information for the insight into the mechanisms of pain/drug abuse brains in order to advance long-term prevention, diagnosis, prediction and treatment planning. Our strategy for analyzing these large complexes imaging datasets will involve four steps: **First step**, preprocess imaging datasets for individual subjects and then convert voxelwise imaging parameters into standard imaging matrices in MNI templates. **Second step**, conduct group-level statistical analysis based on each of imaging modalities, e.g. functional (R-fMRI) or ASL-CBF images. There are three levels of neural network analyses: 1) Seed-based network analysis; 2) ROI-based large scale network analysis; and 3) whole brain Graph theory analysis (e.g., Small-world graphical analysis). From the second step, we will obtain imaging parameters as independent variables for each subject such as brain atrophy, CBF and functional connectivity index (FCI) at seed, regions, and whole brain networks levels. **Third step**, construct a database containing demographic information and a battery of neuropsychological and behavioral testing scores. **Fourth step**, conduct Data fusion processes from step 2 and step 3 with **Multivariate analysis** and **Multivariate Linear Regression for establishing the neural biomarker for diagnosing and measuring treatment responses/efficacy**.

Multivariate analysis will be employed in determining the sensitivity and specificity in discriminating normal, pain, or drug abuse subjects as described in specific Aims. The imaging parameters ***P*** from step 2 (e.g. Functional connectivity index (FCI) and metabolic information (CBF) will be statistically combined to give a composite imaging Index, which will be employed in disease diagnoses. We propose to use a multivariate classification

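### The plan describes two incompatible resting-state acquisitions, and the only one with stated geometry spans 65.1 mm, too little for the whole-brain network analyses it lists

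*Combined protocol and SAP*

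**What the plan says.** All locations are in section F of the combined protocol and SAP.

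- **Multimodal Imaging protocols, R-fMRI item.** The resting-state data are to be analysed at seed, module and whole-brain level: "whole brain network-based analyses to characterize the changes in nausea/pain brains". The next sentence assigns the acquisition to SCITH, a multi-echo sequence developed in-house. The coil for this section is a 32-channel array. No slice count, thickness, gap, TR or TE is given.
- **Data Acquisition and Analysis.** The resting scan for all subjects is gradient EPI with one echo time (25 ms). On the coil: "A quadrature birdcage head coil will be used for radio frequency (RF) transmission and reception". On the images: "One hundred and twenty T2*- weighted images depicting blood oxygenation level-dependent (BOLD) contrast" that "will be acquired over 6 min at each of 14 near-axial non-contiguous 4 mm thick planes parallel to the inter commissural" line, with "TR (repetition time) = 2 s", "FOV (Field of view) = 240 mm" and "interslice gap = 0.7 mm".
- **Optional fMRI sub-study.** This repeats the 64 x 64 matrix, the 2 s TR and the 25 ms echo time. The only scan it calls whole-brain is the anatomical one.
- **fMRI analyses.** Three levels of network analysis are listed, the third being "whole brain Graph theory analysis (e.g., Small-world graphical analysis"). A connectivity index at seed, region and whole-brain level is then taken for each subject and carried into the discriminant function and the multivariate regression.
- **fMRI-guided connectivity analysis.** The amygdala is the seed. The targets are prefrontal areas, insula and hypothalamus.

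**The concern.** A scan operator needs one prescription, and the plan gives two that differ in sequence, number of echoes and coil. Only the EPI version states slice geometry, so it is the one that could be followed from the text. Fourteen thin slices make a slab, yet the analysis sections treat the resting data as covering the whole brain.

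If the slab is acquired and the analysis list is followed, the graph measures and the whole-brain connectivity index will be computed on part of the brain. The plan fixes the slab's orientation but not its vertical position. The part covered could therefore differ between subjects, or between the baseline and post-treatment scans. With 15 subjects per group, uneven coverage could resemble a connectivity difference. Tissue that was not scanned cannot be recovered by imputation or reanalysis.

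**Working it through.** **Inputs, all from Data Acquisition and Analysis:** n = 14 slices, thickness t = 4 mm, gap g = 0.7 mm, field of view 240 mm, matrix 64, TR 2 s, 120 images, 6 min. The plan states no coverage figure to reproduce. The brain's height along the slice direction, H, is not in the documents; I assume 100 to 140 mm and add 80 mm as a case favourable to the plan.

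**1. Check of a figure the plan does state.** In-plane resolution = 240 / 64 = 3.75 mm, which agrees with the text.

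**2. Slab extent.** n x t + (n - 1) x g = 14 x 4 + 13 x 0.7 = 56.0 + 9.1 = 65.1 mm. Counting a trailing gap gives 14 x 4.7 = 65.8 mm. The tissue actually sampled is 56.0 mm.

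**3. Coverage and slices needed.** Share covered = 65.1 / H. Slices needed = (H + 0.7) / 4.7, rounded up.

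| Assumed H (mm) | Share covered | Slices needed |
|---|---|---|
| 80 | 81.4% | 18 |
| 100 | 65.1% | 22 |
| 110 | 59.2% | 24 |
| 120 | 54.2% | 26 |
| 130 | 50.1% | 28 |
| 140 | 46.5% | 30 |

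Fourteen slices are too few at every height in the table.

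**4. Timing in the same sentence.** 6 min = 360 s. At a TR of 2 s that gives 360 / 2 = 180 images. The stated 120 images would need either a TR of 360 / 120 = 3 s or a scan of 120 x 2 = 240 s = 4 min. One of the three figures is wrong.

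**5. Room for more slices.** At a TR of 2 s, 22 slices leave 2000 / 22 = 90.9 ms each and 30 slices leave 2000 / 30 = 66.7 ms each, against one echo at 25 ms. This suggests that extra slices would fit a single-echo scan. It does not settle the matter: step 4 puts the TR in doubt, and a multi-echo sequence needs more time per slice.

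**6. The two descriptions side by side.**

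| | Multimodal Imaging protocols | Data Acquisition and Analysis |
|---|---|---|
| Sequence | SCITH, multi-echo | Gradient EPI, one echo (25 ms) |
| Coil | 32-channel array | Quadrature birdcage |
| Coverage | Not stated | 65.1 mm |

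No statement says which governs.

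**The case against.** The strongest objection is that the whole-brain analyses are announced in the same paragraph as SCITH, not beside the EPI geometry. A reader might infer from the 14 slices that the whole-brain analyses cannot be run on the data to be collected. The documents do not support that: if SCITH governs, coverage is unknown, and it may be adequate. This stands. It does not clear the plan, because in that case the required coverage is unspecified and the EPI paragraph is wrong. Two sections also give the EPI parameters, while none gives any for SCITH.

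A reader might also infer that Aims 2 and 3b are lost. They concern vmPFC-amygdala connectivity, which is a seed analysis, and a suitably placed 65 mm slab may contain both regions. Nothing in the documents shows otherwise. The whole-brain graph analysis carries no hypothesis of its own in section B, and the imaging is an optional sub-study.

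A shift in slab position between scans is a possibility inferred from silence. The plan does fix the orientation and says that the same protocol is repeated after therapy. The gaps between slices are openly stated and contradict nothing.

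**Conclusion.** The concern holds as an internal inconsistency. The plan gives two resting-state acquisitions that cannot both be used. The only one with stated geometry spans 65.1 mm, about 46% to 65% of an assumed 100 to 140 mm brain height, and does not fit the whole-brain network and graph analyses. The percentages rest on that assumed height, but the shortfall remains even at 80 mm. The image count, TR and scan length in the same sentence also disagree.

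What will be collected is undetermined; it is not established that it will be a partial brain. The amygdala-vmPFC analysis is not ruled out by slab height, although its coverage is not secured while the slab's position is left open. Severity is moderate and confined to the optional imaging sub-study. The primary outcome, the Nausea Severity Scale, is unaffected.

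**What to change.** Before the first scan:

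1. Name the one governing resting-state sequence and coil, and remove the other description. Changing 14 to a larger number is not enough while two acquisitions remain.
2. Then take one of two routes.
   - **Whole-brain coverage.** State the slice count, thickness and gap of the governing sequence so that they cover the whole brain. At the stated 4.7 mm spacing this is about 22 to 30 slices for 100 to 140 mm. Confirm on the scanner that this is feasible at the chosen TR.
   - **Keep the 14-slice slab.** Fix its position on anatomical landmarks so that the amygdala and vmPFC are covered at both scans. Delete the whole-brain network and graph analyses from Multimodal Imaging protocols and fMRI analyses, and delete the whole-brain connectivity index from fMRI analyses.
3. Reconcile the number of images, the TR and the scan length.

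The cost is a few lines of protocol text and a scanner prescription. Added scan time looks unlikely for a single-echo scan at a TR of 2 s, subject to the scanner check. The second route adds no scanning but gives up the whole-brain outputs.
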